A simple randomization method was used to randomly allocate patients in a 1:1 ratio to the conventional ventilation group or the INTELLiVENT-ASV group. Randomization was performed using the list randomizer on the website www.random.org. Randomization and allocation was performed immediately after the informed consent form was signed and the allocation of the patient was known only at the moment of the randomization. A hardcopy of the randomization outcome was printed with timestamp, signed and archived.

The physician and the team caring for the patients were not blinded. The researcher performing the data analyses, the radiologist that evaluates the postoperative chest X-rays, and the statistician performing the data analyses will be blinded.

The ventilation strategies

Patients randomized to the conventional ventilation group received a continuous mandatory volume or pressure controlled ventilation, if they were not breathing spontaneously, immediately after the admission in the ICU. Based on physician criterion ventilator settings were set by the anesthesiologist in consultation with the intensivist and ICU nurse on duty during the postoperative handover.

Pressure support mode was selected if patients were breathing spontaneously during handover. After the handover the ICU nurse or ICU physician could adjust ventilator settings during mechanical ventilation. If needed the ICU nurse could always consult the ICU physicians on duty. It was not possible to extubate the patient without consulting the ICU physician on duty, who made the final call to extubate. Spontaneous breathing trials (SBT) were not applied during the first three hours of mechanical ventilation. The patient was extubated without a SBT if the physicians decided that the patient could be extubated within the first three hours of mechanical ventilation. Postoperative ventilation and weaning was performed based on local hospital protocols that targets lung protective ventilations with a target tidal volume of 6ml/kg of PBW. The standard operating procedure is described in appendix 1. The predicted body weight (PBW) that is used in table 3 is calculated according to a previously used formula [5]:

- $50 + 0.91 \times (\text{centimeters of height} - 152.4)$ for male; and
- $45.5 + 0.91 \times (\text{centimeters of height} - 152.4)$ for females.

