The ventilatory variables will be extracted from the datalogger output files and transferred to the databases that will be exported for statistical analysis. After that, these study databases will be locked and exported for statistical analysis to the Academic Medical Center, Amsterdam, The Netherlands. The results of this analyses will be documented in a comprehensive database. At this stage, this last database will be locked as soon as all data are entered and all discrepant or missing data are resolved – or if all efforts are employed and remaining issues cannot be fixed. At this step, the data will be reviewed before database locking. At this stage, permission for access to the database will be removed for all investigators, and the database will be archived.

Missing data

No or minimal missing for the primary and secondary outcomes are anticipated, except for the quality and number of SpO₂ measurement in the datalogger. These measurement are assessed with fingertip pulse oximeter that sometimes cannot assess a value or the quality of the assessment is not sufficient. Breaths with missing SpO₂ or a quality of the assessment of < 51% will be excluded from the analyses of the primary and secondary outcomes where this measurements are necessary.

Sample size

A power analysis was performed using G*Power (version 3.1.9.2.; Franz Faul, Universitet Kiel, Duitsland). Based on this analysis the trial was designed to enroll at least 196 patients in total. This number of patients was expected to be sufficient to detect a reduced ventilation time of 14.0 minutes in the unacceptable zone in the INTELLiVENT-ASV group considering a common standard deviation of 10.0 minutes [4], a type I error of 5%, 95% of power, similar allocation of subjects to each group and corrected for dropouts.

Predefined statistical analysis plan

There were no major adjustments from the preliminary analysis plan, as reported previously in the online accessible protocol [1]. In accordance, all statistical analyses will be conducted according to an intention-to-treat principle, considering all patients in the treatment groups to which they were randomly assigned.

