Visual inspection of histograms and D'Agostino–Pearson's normality tests will be used to assess continuous distribution of the data. For the conventional ventilation and INTELLiVENT-ASV arms, the baseline characteristics will be expressed as counts and percentages, means and standard deviations (SD), or medians and interquartile ranges (IQR) whenever appropriate. Hypothesis tests will be two-sided with a significance level of 5%. We will not adjust P -values for multiple comparisons. Analyses will be performed using the R (R Core Team, 2016, Vienna, Austria) program.

Trial profile: Patient flows will be presented in a CONSORT flowchart (Figure 1).

Baseline comparisons: Patient's baseline characteristics will be presented by study arm (eTable 2).

Adherence to study interventions and, ventilator variables and vital signs:

Ventilatory variables and vital signs will be reported from ICU admission until extubation or up to the first 72hours of recorded mechanical ventilation time (eTable 3). These variables, including driving pressure and mechanical power, will be compared among the groups using Student's *t* test. Also, the trend of the ventilator variables every 30 minutes for the first three hours will be compared between the groups using mixed-effect linear models, considering an interaction term between time and group and the patients as random effects.

Outcomes:

Percentage of time in the optimal, acceptable and unacceptable zone for at least 30 seconds during the first three hours of ventilation or until extubation, if extubated earlier, and according to the postoperative total recorded ventilation time (eTable 4).

The number of episodes where the ventilation stays in one of the three zone for at least 30 consecutive seconds will be calculated. Then, this number will be corrected by the total duration of ventilation as:

$$\%_{UZ} = (T_{UZ} / DV) \times 100$$

Where $\%_{UZ}$ is the percentage of time in a zone, T_{UZ} is the time in seconds where the ventilation stays in the specific zone for at least 30 consecutive seconds, and DV is the total duration of ventilation in seconds. This number will be reported as mean \pm standard deviation and median (interquartile range). The effect of the intervention will be estimated with a Student's *t*-test and reported as the mean difference between the two groups. The consistency of the findings of the Student's *t*-test will be tested using a bootstrapped Student's *t*-test with 1,000

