replications. If a very nonsymmetrical distribution is found, we will use the best distribution that fits the data.

Percentage of breaths in the optimal, acceptable and unacceptable zone according to the total number of breaths during the first three hours of ventilation or until extubation, if extubated earlier, and according to the postoperative total recorded ventilation time. (eTable 4).

The percentage of breaths in the three zones will be reported as number and percentages (according to the total number of breaths and not according to the number of patients) and the effects of the intervention will be estimated with risk ratio and 95% confidence intervals calculated with Wald's likelihood ratio approximation test and with χ^2 tests for hypothesis testing.

Number of successful extubations within the first 6, 12 and 24 hours after surgery (eTable 5).

The effects of the intervention on the number of successful extubation within the first 6, 12 and 24 hours of mechanical ventilation after admission on the ICU will be reported as number and percentages and estimated with risk ratio and 95% confidence intervals calculated with Wald's likelihood ratio approximation test and with χ^2 tests for hypothesis testing. These findings will be confirmed using logistic models adjusted by the duration of surgery, total intravenous sedatives dosage and the time from ICU admission until a rectal temperature $>35.5^{\circ}\text{C}$.

Total Time until extubation (considering the time from ICU admission until extubation) (eTable 5).

The time until extubation will be assessed using Kaplan–Meier curves, and hazard ratios with a 95% confidence interval will be calculated with Cox proportional hazard models without adjustment for covariates. The proportional hazard assumptions will be tested and alternative parametric survival models will be used if the proportionality assumption is not sustained. These findings will be confirmed using Cox proportional hazard models adjusted by the duration of surgery, total intravenous sedatives dosage and the time from ICU admission until a rectal temperature $>35.5^{\circ}\text{C}$.

Time until first spontaneous breathing (considering the time from ICU admission until first spontaneous breathing) (eTable 5).

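### Student's t-test for the primary mean difference makes no provision for unequal arm SDs under simple randomisation; naming Welch's test is a minor improvement at almost no cost

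*Combined protocol and SAP*

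**What the plan says.** In the SAP's Outcomes section, the entry for percentage of time in each zone states: "The effect of the intervention will be estimated with a Student's" t-test, with the effect "reported as the mean difference between the two groups". eTable 4 gives this estimate a 95% confidence interval in the intention-to-treat, as-treated and per-protocol columns. The same test is named for the number of alarms and interventions, for the nurse acceptance score, and for ventilator variables and vital signs.

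Two supporting provisions follow for the primary outcome. The first is a check: "The consistency of the findings of the Student's" t-test is to be examined with a bootstrapped Student's t-test of 1,000 replications. The second is a fallback: "If a very nonsymmetrical distribution is found, we will use the best distribution that fits the data".

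On arm sizes, Randomization and blinding says: "A simple randomization method was used to randomly allocate patients in a 1:1 ratio". No blocking or stratification is described. On variability, Sample size gives one figure for both arms: "considering a common standard deviation of 10.0 minutes". No arm-level mean or SD appears, and neither unequal variances nor a robust standard error is mentioned.

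**The concern.** The pooled standard error is right when the two SDs are equal, and is essentially right when the two arms are the same size. The plan secures neither condition. Simple randomisation lets the arm sizes drift. The outcome cannot fall below zero, and the trial is designed to "detect a reduced ventilation time of 14.0 minutes in the unacceptable zone" in one arm. An arm close to that floor would plausibly have the smaller SD. The Subgroup analyses section itself anticipates zero-inflated distributions for the primary outcome.

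If both conditions fail together, the direction of the error depends on chance. The interval is too narrow when the less variable arm is the larger, and too wide when it is the smaller. What is at stake is the accuracy of the reported 95% interval for the realised split. The provisions in the plan do not clearly deal with this. The bootstrap is of the same named statistic with no stated resampling scheme, and the fallback is triggered by asymmetry, not by unequal variance.

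**Working it through.** **Inputs.** From Sample size: "the trial was designed to enroll at least 196 patients in total", a difference of 14.0 minutes, a common SD of 10.0 minutes, two-sided 5% (from the SAP) and 95% power. From Randomization and blinding: simple 1:1 allocation. Assumed, because the documents do not give it: an SD ratio between arms of 2 to 3, set here as 10 against 5 or 3.33 minutes.

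**The plan's own figure.** n per arm = 2 × (1.960 + 1.645)² × (10/14)² = 13.3, so 14 per arm and 28 in total (30 with the t distribution). The stated 196 does not follow from these inputs unless dropout is about 85%. That is a separate matter. Here 196 is simply the planned total, since the documents do not give the numbers per arm.

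**Arm sizes.** With Binomial(196, 0.5), an arm lies 7 or more from 98 with probability 35%, and 14 or more with probability 5%. Undercoverage needs the imbalance in one particular direction, so those chances are about 18% and 2.7%.

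**Standard errors.**
- Pooled: SE_p = √[s_p²(1/n₁ + 1/n₂)], with s_p² = [(n₁−1)s₁² + (n₂−1)s₂²]/(n₁+n₂−2).
- True: SE = √(s₁²/n₁ + s₂²/n₂).
- Approximate coverage of the pooled interval: 2Φ(1.96 × SE_p/SE) − 1.

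Worked case, SD ratio 2, with 112 in the less variable arm and 84 in the other:
- s_p² = (83 × 100 + 111 × 25)/194 = 57.1
- SE_p = √[57.1 × (1/84 + 1/112)] = 1.091
- SE = √(100/84 + 25/112) = 1.189
- ratio 0.917, coverage 92.8%

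| Less variable / more variable arm | SE_p/SE, SD ratio 2 | Coverage | SE_p/SE, SD ratio 3 | Coverage |
|---|---|---|---|---|
| 98 / 98 | 1.000 | 95.0% | 1.000 | 95.0% |
| 105 / 91 | 0.958 | 94.0% | 0.944 | 93.6% |
| 112 / 84 | 0.917 | 92.8% | 0.891 | 91.9% |
| 91 / 105 | 1.044 | 95.9% | 1.059 | 96.2% |
| 84 / 112 | 1.090 | 96.7% | 1.122 | 97.2% |

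**Average over simple randomisation.** Weighting the same coverage formula by the binomial probabilities gives 94.9% at either SD ratio. Coverage falls below 93% in 3.7% of allocations at SD ratio 2 and in 8.7% at ratio 3.

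**Simulation check (20,000 trials per setting).** At 112/84 and SD ratio 2, the pooled interval covered 92.5% with normal data and 92.4% with gamma data. Welch's interval covered 94.7-95.3% in every setting run, up to an SD ratio of 5. Its critical value exceeded the pooled one by at most 0.8%.

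**Effect on the conclusion.** With 98 per arm and SD 10, SE = 10 × √(2/98) = 1.43 minutes, so the planned 14.0 minutes is 9.8 standard errors. A standard error wrong by 4-12% would not change that result.

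**The case against.** The strongest reply is that a reader might infer that the primary interval lacks its stated coverage, and the documents do not show this. It needs unequal SDs and unequal arms together. The sample-size text assumes a common SD and similar allocation, and no arm-level figures are given. At equal arms the pooled interval is nominal whatever the SD ratio, and over the randomisation actually used it averages 94.9%. This stands in full and limits the point to the realised split.

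A reader might also infer that the problem grows in the subgroup analyses. The documents do not support that. Subgroup effects are to be evaluated through interaction terms in generalized linear models, not through t-tests, and no subgroup sizes by arm are given.

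Three further replies have partial force:
- **Skewness fallback.** The mechanism that would make the SDs unequal, an arm pressed against zero, also produces skewness, so the fallback may replace the t-test altogether. It may. But its trigger is not defined, and it does not address unequal variances as such.
- **Software default.** The SAP never says pooled, and the analysis is to be run in R, whose standard t-test function defaults to the unequal-variance version. The intended analysis may therefore already be Welch's. Even so, the named test is conventionally the pooled one, and the plan should settle which is meant.
- **Bootstrap.** The scheme is unstated, so it cannot be assumed to share the fault. Equally, it cannot be assumed to correct it, and it is not said to supply the interval in eTable 4.

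**Conclusion.** The point holds as a minor improvement in interval accuracy at almost no cost. The plan names a test that conventionally pools variances, lets arm sizes vary by chance, and says nothing about unequal SDs. If the SDs differ by a factor of 2 to 3 and the arms come out uneven, actual coverage would be roughly 92-94% in the unfavourable direction and 96-97% in the other, for splits between 105/91 and 112/84 either way. These figures rest on the assumed SD ratio and on 196 patients analysed. They do not establish that the primary interval is wrong, and the primary conclusion at the planned effect would be the same under either test. The reason to act now is that the SAP aims to exclude data-driven choices, and choosing between the two tests after seeing the arm SDs would be such a choice.

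**What to change.** In the Outcomes section, replace Student's t-test with Welch's (unequal-variance) t-test for the primary outcome and for the other mean differences: alarms, interventions, acceptance score and ventilator variables. Apply the same wording to the per-protocol and as-treated comparisons in eTable 4. State that the bootstrap resamples patients within each arm and uses the Welch statistic.

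The cost is one phrase for the test and one for the bootstrap, plus one explicit option in R. No new data are needed. With equal arms and equal SDs the result is essentially unchanged.

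### The primary comparison is a valid but unadjusted t-test after simple randomisation; prespecifying a few pre-randomisation covariates would cost almost nothing and may add precision and protection against chance imbalance

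*Combined protocol and SAP*

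**What the plan says.** Under Randomization and blinding: "A simple randomization method was used to randomly allocate patients in a 1:1 ratio". No stratification or blocking is mentioned. Allocation followed immediately on consent, which Eligibility of the patients places on the day before surgery.

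Under Predefined statistical analysis plan, Outcomes, the percentage of time in each zone (%UZ for the unacceptable zone) is compared by a Student's t-test and "reported as the mean difference between the two groups". Two supports are given: a bootstrapped t-test with 1,000 replications, and the rule "If a very nonsymmetrical distribution is found, we will use the best distribution that fits the data". Neither brings in covariates. Patient factors meet the primary outcome only in the Subgroup analyses, as median splits tested by interaction. These do not adjust the overall effect.

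Three secondary outcomes do have adjusted confirmatory models. For successful extubation the SAP writes "These findings will be confirmed using logistic models adjusted by the duration of surgery", then adds total sedative dose and time to rewarming. Time to extubation and time to spontaneous breathing use the same three covariates.

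The baseline table (eTable 2) already collects BMI, sex, predicted body weight (PBW) and COPD history. The zone table (eTable 1) expresses the tidal-volume limits per kg PBW.

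**The concern.** Simple randomisation balances prognostic factors only on average. In a single trial of this size, moderate imbalance in one factor or another is common. An unadjusted mean difference carries such an imbalance in proportion to how strongly the factor predicts the outcome. A prespecified linear adjustment removes that part, keeps the mean difference as the estimand, and narrows the interval if the covariates are prognostic.

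Timing also matters. The SAP says it was drafted without knowledge of outcome data and before database lock, so a covariate list fixed now is credible. If imbalance is first noticed when the baseline table is filled, any adjustment will be post hoc, which is what the document says it exists to prevent.

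**Working it through.** **Inputs.** From Sample size: at least 196 patients, equal allocation (98 per arm if the split is exact), "a type I error of 5%, 95% of power", power to "detect a reduced ventilation time of 14.0 minutes in the unacceptable zone", and a "common standard deviation of 10.0 minutes". Tests are two-sided. R², the share of outcome variance explained by the covariates, is not given; 0 to 0.30 is assumed. The stated SD is in minutes while the endpoint is a percentage, so results in minutes are illustrative. The ratios do not depend on the scale.

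**The plan's own figure.** n per arm = 2(1.960 + 1.645)² × (10/14)² = 13.3, so 14 per arm and 28 in total (15 per arm, 30 in total, with the t distribution). The stated inputs therefore do not give 196 unless dropout is about 85%. That is a separate matter and does not decide this point. Under those inputs, power with 98 per arm exceeds 99.99%.

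**Precision.** Unadjusted SE = 10 × √(2/98) = 1.43 minutes. Adjustment multiplies this by √(1 − R²) and by a cost for estimating k covariates, √(193/(193 − k)). For k = 3 the cost is √(193/190) = 1.008; for k = 4 it is √(193/189) = 1.011.

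| Assumed R² | SE ratio, no cost | SE ratio, 3 covariates | Equivalent N = 196/(1 − R²) |
|---|---|---|---|
| 0 | 1.000 | 1.008 | 196 |
| 0.05 | 0.975 | 0.982 | 206 |
| 0.10 | 0.949 | 0.956 | 218 |
| 0.20 | 0.894 | 0.901 | 245 |
| 0.30 | 0.837 | 0.843 | 280 |

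**Chance of imbalance.** For a factor present in 50% of patients, the SD of the between-arm difference is √(0.5/98) = 7.1 points. P(|difference| ≥ 10 points) = 2 × [1 − Φ(10/7.1)] = 2 × [1 − Φ(1.4)] = 0.16. Ten points is 0.2 SD of such a factor, since its SD is 0.5. For at least one of three independent covariates to differ by more than 0.2 SD, the probability is 1 − (1 − 0.16)³ = 0.41.

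**Effect of that imbalance on the estimate.** The difference in outcome between patients with and without the factor is √R² × 10/0.5 minutes, and the shift is 0.10 times that.
- R² = 0.05: 0.10 × 0.224 × 20 = 0.45 minutes, or 0.45/1.43 = 0.3 SE.
- R² = 0.30: 0.10 × 0.548 × 20 = 1.10 minutes, or 1.10/1.43 = 0.8 SE.

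Against the 14-minute target these are about 3% and 8%.

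**Conditional type I error.** With shift b and residual standard error s = 1.43 × √(1 − R²), the unadjusted test rejects a true null with probability 1 − Φ((1.96 × 1.43 − b)/s) + Φ((−1.96 × 1.43 − b)/s). Given a 0.2 SD imbalance, this is 5.5%, 6.1%, 7.0% and 7.7% for R² of 0.05, 0.10, 0.20 and 0.30. Averaged over all randomisations it stays at 5%.

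**The case against.** The strongest reply is that this is a preference and not an error. An unadjusted t-test after simple randomisation is unbiased over randomisations, with 5% overall type I error. That stands. A reader might infer that the primary analysis is biased or invalid; the documents do not support that.

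A reader might also infer that a known amount of precision is being given away free. That does not hold either. The gain rests wholly on an assumed R², and there are reasons to expect a modest one. Eligibility caps BMI below 35 kg/m² and excludes GOLD 3 and 4, so the COPD item in eTable 2 reduces to GOLD 2. The subgroup models for this outcome allow for zero inflation, which makes a high linear R² less likely.

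It is tempting to argue that PBW must predict the outcome because the tidal-volume limits are indexed to it. Indexing is size normalisation and may weaken the dependence on body size, and the local ventilation target is also set per kg PBW. No document shows that PBW is prognostic here.

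It is equally tempting to call the SAP inconsistent because it adjusts the extubation outcomes. Those models are a poor precedent. They are outcome-specific, and all their covariates arise after randomisation, two of them potentially after the assigned mode has started.

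Finally, under the plan's stated effect and SD, power is already near 100%. This is fair, but it leans on inputs that do not reproduce the sample size. Chance imbalance moves the estimate whatever the power.

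**Conclusion.** The point holds as a missed improvement of minor weight. The planned analysis is sound, but it forgoes possible precision and conditional protection that variables already in the baseline table could give. Across an assumed R² of 0 to 0.30, the SE would go from about 1% wider to about 16% narrower. A 10-point imbalance in a 50% factor, which has about a 16% chance of arising, would shift the estimate by a fraction of a standard error if that factor explained 5% to 30% of the variance. These figures assume 98 analysed patients per arm. The R² range is an assumption, so the documents cannot say whether the real gain is worthwhile or close to nil. What can be said is that the possible loss from adjusting is small and bounded.

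**What to change.** Before unblinding, add to the primary outcome analysis a linear model of %UZ on arm plus a short, named list of variables fixed before randomisation: for example BMI, PBW (or sex and height in its place) and COPD history. Sex and PBW should not both be listed without thought, because PBW is computed from sex and height. Use robust or bootstrap standard errors, since the outcome may be skewed, and report the adjusted mean difference alongside the unadjusted one.

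The criterion for inclusion should be that the variable was fixed before randomisation; being fixed before ICU ventilation is not enough in this trial. Because patients were randomised on consent before surgery, duration of surgery, sedative dose and time to rewarming should be omitted.

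The cost is a sentence or two in the SAP and no new data collection. The downside is having to settle the covariate list in advance, and a loss of roughly 1% in SE if the covariates turn out not to be prognostic.

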Patients randomized to the INTELLiVENT-ASV group received this mode of ventilation immediately after the admission in the ICU. Quickwean was immediately activated at that time, but the SBT mode was switch off for the first three hours of mechanical ventilation. It was not possible to extubate the patient without consulting the ICU physician on duty, who made the final call to extubate. Spontaneous breathing trials (SBT) were not applied during the first three hours of mechanical ventilation. The patient was extubated without a SBT if the physicians decided that the patient could be extubated within the first three hours of mechanical ventilation. After the first three hours of ventilation the SBT function

of INTELLiVENT-ASV was initiated and the patient could be extubated if the patient had a successful SBT of at least 10 minutes with a consultation of the ICU physician on duty. The standard operating procedure is described in appendix 2.

In both arms it was possible to deviate from protocol if the ICU physician deemed it necessary for the safety of the patient. In these cases the patient could be switched to the not allocated mode.

In both arms the same alarm settings were used, which were: 1) pressure alarm ≥ 35 cmH₂O; 2) expiratory minute volume alarm ≤ 3.0 and ≥ 15.0 L/min; 3) respiratory rate alarm ≥ 35 breaths per min; 4) tidal volume alarm ≥ 900 ml; 5) apnea time alarm ≥ 30 seconds; 6) EtCO₂ alarm ≤ 30 and ≥ 60 mmHg; and 7) SpO₂ alarm $\leq 90\%$.

Outcomes

Primary outcome:

1. Percentage of time (during at least 30 seconds) in the unacceptable zone according to the total postoperative ventilation time on the ICU during the first three hours of ventilation or until extubation, if extubated earlier.

Secondary outcomes:

1. Percentage of time (during at least 30 seconds) in the optimal and acceptable zone according to the total postoperative ventilation time during the first three hours of ventilation or until extubation, if extubated earlier.
2. Percentage of breaths in the optimal, acceptable and unacceptable zone according to the total number of recorded breaths during the first three hours of ventilation or until extubation, if extubated earlier.

3. Percentage of time (during at least 30 seconds) in the optimal, acceptable and unacceptable zone according to the total number of recorded time.
4. Percentage of breaths in the optimal, acceptable and unacceptable zone according to the total number of recorded breaths.

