5. Ventilator variables and vital signs will be reported after each half an hour from ICU admission until spontaneous breathing (>5 consecutive spontaneous breaths) or the first three hours of mechanical controlled ventilation. Ventilator variables include the manually measured tidal volume, driving pressure and mechanical power. Driving pressure will be calculated by extracting the PEEP after >5 seconds of an expiratory hold from the plateau pressure level after >5 seconds of an inspiratory hold. Both this recorded PEEP and plateau pressure were used with other manually recorded parameters to calculate the mechanical power:

$$\text{Power}_{rs} = RR \cdot \{\Delta V^2 \cdot [0.5 \cdot EL_{rs}] + (RR \cdot ((1+I:E)/(60 \cdot I:E)) \cdot R_{aw})\} + \Delta V \cdot PEEP\}. [6]$$

Vital signs include also EtCO₂: PaCO₂ and PaO₂: FIO₂ ratio that were conducted at admission and after approximately an hour of ventilation.
6. The number patients extubated in the first six, twelve and twenty-four hours after surgery without a reintubation or non-invasive ventilation ≤48 hours after extubation for respiratory insufficiency (a successful extubation).
7. Ventilation time considered as the time from intubation during surgery until first and first successful extubation adjusted by the duration of surgery.
8. Weaning duration considered as the time from stopping intravenous sedatives and a rectal temperature of ≥35.5°C since admission on the ICU until successful extubation.

9. The time from intubation during surgery until spontaneous breathing (at least ≥ 5 consecutive spontaneous breaths) adjusted by the duration of surgery.
10. The time from stopping intravenous sedatives with a rectal temperature of $\geq 35.5^{\circ}\text{C}$ during admission on the ICU until spontaneous breathing (at least ≥ 5 consecutive spontaneous breaths).
11. The total number of alarms and interventions per hour within the first 3 hours or until extubation.
12. The total number of alarms and interventions per hour according to the total registered ventilation time.
13. ICU mortality
14. 30 day mortality
15. The number of ICU readmissions during the first 72 hours after ICU discharge.
16. ICU length of stay.
17. The number of agitated moment, established by the nurse at the bedside.
18. The number of bolus administration of sedatives and analgesics.

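### The adjusted logistic check on successful extubation at 6, 12 and 24 h cannot confirm the size of the planned risk ratio unless extubation is uncommon; a standardised risk ratio, over covariates the ventilation mode cannot affect, would

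*Combined protocol and SAP*

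**What the plan says.** Secondary outcome 6 is a yes/no result for each patient at three time points: "The number patients extubated in the first six, twelve and twenty-four hours after surgery", with no reintubation or non-invasive ventilation for respiratory insufficiency in the following 48 hours.

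The SAP paragraph on successful extubations gives the main estimate as an unadjusted comparison, "estimated with risk ratio and 95% confidence intervals calculated with Wald's likelihood ratio approximation test", with a chi-square test. The supporting analysis follows: "These findings will be confirmed using logistic models adjusted by the duration of surgery", together with the total dose of intravenous sedatives and the time between ICU admission and a rectal temperature above 35.5 °C.

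The paragraph does not say which effect measure the logistic model will report or what would count as confirmation. It plans no standardised risk ratio, log-binomial model or modified Poisson model. As far as eTable 5 can be read, it has no row for this outcome and no column for adjusted estimates, so it does not settle the matter.

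The other confirmations in the SAP keep their effect measure. A mean difference from a t-test is checked by a bootstrapped t-test, and an unadjusted hazard ratio by an adjusted hazard ratio. Here the measure changes.

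A separate matter for the authors to reconcile is the clock, which starts after surgery in the outcome list but after ICU admission in the analysis paragraph ("of mechanical ventilation after admission on the ICU will be reported as number and percentages and estimated with risk ratio").

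**The concern.** A risk ratio and an odds ratio for the same data agree closely only when the event is rare. As the event becomes common, the odds ratio moves further from 1 than the risk ratio. Adding prognostic covariates moves the conditional odds ratio a little further again, even when the arms are perfectly balanced (non-collapsibility). A gap between the two figures is therefore no evidence that adjustment changed the effect, and similar figures would be no evidence that it did not.

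If the two estimates are printed together, a modest risk ratio could stand beside an adjusted figure near 2 and be read as a much larger effect, or two consistent results could look discordant. Extubation is a secondary endpoint named in the abstract, so readers will look at it.

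A second issue is practical. If nearly all patients are extubated by 24 h, few non-events remain to support a model with treatment and three covariates.

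**Working it through.** **Inputs.** The documents give no extubation rate and no design figure for this endpoint, so there is no stated result to reproduce. From the documents come the effect measures, 1:1 allocation, and the planned total of 196, that is 196/2 = 98 per arm. The event rates and covariate strengths below are assumptions, shown as a range.

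**Step 1: odds ratio against risk ratio.** With control risk p0 and intervention risk p1, RR = p1/p0 and OR = [p1/(1−p1)]/[p0/(1−p0)]. For 60% versus 75%: RR = 0.75/0.60 = 1.25 and OR = (0.75/0.25)/(0.60/0.40) = 3.0/1.5 = 2.00. For 90% versus 95%: RR = 0.95/0.90 = 1.06 and OR = 19/9 = 2.11.

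**Step 2: shift from adjustment.** Let logit P(extubated) = a_g + L, where g is the arm and L is the covariate contribution. Assume three independent standard normal covariates with log-odds slopes 0.6, 0.5 and 0.4, so the SD of L is √(0.36 + 0.25 + 0.16) = √0.77 = 0.88. Choose a_0 and a_1 so that the risks averaged over L equal p0 and p1. The conditional OR is exp(a_1 − a_0).

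| Control vs intervention | RR | Unadjusted OR | Conditional OR |
|---|---|---|---|
| 10% vs 12.5% | 1.25 | 1.29 | 1.31 |
| 30% vs 37.5% | 1.25 | 1.40 | 1.47 |
| 50% vs 62.5% | 1.25 | 1.67 | 1.81 |
| 60% vs 75% | 1.25 | 2.00 | 2.22 |
| 90% vs 95% | 1.06 | 2.11 | 2.21 |

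Most of the gap is plain OR versus RR; non-collapsibility adds the smaller part. Conversely, a single OR of 2.0 corresponds to RR 1.82 at a control rate of 10%, 1.33 at 50% and 1.05 at 90%.

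**Step 3: what the check can do.** Simulation of 1,500 trials used 98 per arm, 50% versus 62.5%, and one covariate with SD 1 on the logit scale that treatment does not affect. The chi-square test and the adjusted logistic model agreed in direction in 97% of trials and on significance in 85%. The median unadjusted RR was 1.25, the median adjusted OR 1.86, and the median standardised RR from the same logistic model 1.25.

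**Step 4: which covariates may be standardised over.** Randomisation takes place at consent, the day before surgery. Duration of surgery is fixed before the allocated ICU mode starts. The time to a rectal temperature above 35.5 °C runs from ICU admission, when the mode starts, and sedation on the ICU also accrues from then; the number of sedative boluses is itself a secondary outcome. I took the 60% versus 75% case with the Step 2 slopes and 98 per arm, and let the intervention lower sedative dose by an assumed 0.3 or 0.5 SD. The unadjusted RR averaged about 1.25. The RR standardised over all three covariates averaged about 1.20 and 1.17. Standardised over a covariate that treatment does not affect, it stayed at about 1.25. With no shift in dose, all three estimates agreed.

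**Step 5: few non-events at 24 h.** At an assumed 95% versus 97%, expected non-events are 98 × 0.05 + 98 × 0.03 = 7.8. In 600 simulated trials, 36 adjusted fits failed or gave extreme estimates. At 90% versus 95% (98 × 0.10 + 98 × 0.05 = 14.7 non-events), 5 of 600 did.

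**The case against.** The strongest reply is that the plan never says the logistic model must reproduce the size of the risk ratio. The sentence follows directly on a hypothesis test, and checking that direction and evidence survive adjustment is an ordinary purpose. That stands in part: Step 3 shows that the check does this tolerably well. But the findings to be confirmed include a risk ratio and its interval, and no narrower meaning is given.

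A reader might infer that extubation is known to be common here, so that an adjusted figure near 2 is bound to appear. The documents do not support that, because they state no rate. Extubation before three hours is provided for ("during the first three hours of ventilation or until extubation, if extubated earlier") and surgery is elective, which makes low rates unlikely at 12 and 24 h. At 6 h a low rate is possible, and at 10% the gap is trivial. A reader might also infer that the two estimates will be printed side by side, but eTable 5 as it can be read shows no adjusted column.

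Finally, standardising the model exactly as specified would keep two covariates that treatment may affect. That objection stands in full, and it limits the remedy.

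**Conclusion.** The concern holds as a minor point. The planned logistic check can support the direction and, roughly, the significance of the risk ratio, but it cannot confirm its size unless extubation by that time is uncommon. The mismatch runs from negligible (1.31 against 1.25 at a 10% control rate) to large (2.21 against 1.06 at 90% versus 95%). Where the trial falls in that range depends on rates the documents do not give and, to a lesser degree, on the assumed covariate slopes.

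It would go too far to conclude that the check is worthless or that the main analysis is unsound: the unadjusted risk ratio, its interval and its test are untouched. The use of covariates recorded after the mode has started is a further weakness of the same model. A change of effect measure alone does not cure it, and the 1.20 and 1.17 in Step 4 rest on assumed shifts in dose.

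**What to change.** Amend the sentence to say that the adjusted logistic model will be reported as a standardised (marginal) risk ratio and risk difference. Predict each patient's probability under both arms, average within each assignment, and take the ratio and the difference, with bootstrap or delta-method 95% confidence intervals. Use a Firth-type penalty if non-events are few at 24 h.

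Standardise only over covariates the ventilation mode cannot affect: duration of surgery, or baseline variables already collected. Do not describe a result adjusted for total sedative dosage or time to a rectal temperature above 35.5 °C as a marginal treatment effect. If that model is kept, label it exploratory and name its effect measure.

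The cost is a sentence or two in the SAP, a few lines of R and slightly more analysis work. No new data are needed.
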